7 EXPERIMENTAL PROCEDURES

Screening may begin up to 30 days prior to first dose of study drug. Baseline assessments may be conducted over a 48-hour period prior to the first dose of study drug to allow for scheduling of all activities. Alternately, the Screening and Baseline assessments may be conducted in 1 visit if all assessments are performed and all entry criteria are satisfied within the 48 hours prior to randomization and first dose of study drug.

7.1 SCREENING VISIT

The recommended sequence of assessments for the Screening Visit is as follows (if not combined with the Baseline Visit [see Section 7.3 for the recommended sequence of events for the combined Screening/Baseline Visit]):

- Informed consent
- Inclusion/exclusion criteria review
 - o If necessary, the following procedures may be performed during the 30 day Screening window if required to satisfy inclusion/exclusion criteria (previous medical records documenting eligibility criteria may also be used provided the previous records document subject eligibility within the protocol mandated timelines, as applicable):
 - RHC (Must be performed within 1 year prior to randomization. If a historical RHC is not available in this timeframe, a RHC may be performed during Screening so long as it is performed at least 5 days prior to randomization [Baseline (Day 1)]; a RHC cannot be combined with the Baseline Visit).
 Select RHC parameters will be recorded in the eCRF including: mPAP, PVR, PCWP, and vasodilator response (as applicable).
 - CT scan (must be performed within 6 months prior to randomization). A redacted copy of the CT scan used to confirm subject eligibility should be sent to the Sponsor.
 - Although not required for eligibility, the date of lung biopsy for subjects with a biopsy confirmed diagnosis of ILD will be recorded in the eCRF.
- Demographics
- PH history
- Medical history

- PE
- Vital signs (following at least 5 minutes of rest; collected prior to 6MWT or after recovery from the 6MWT, if practice 6MWT is applicable); including height, weight, RR, HR, systolic blood pressure (SBP), diastolic blood pressure (DBP), and temperature.
- Blood draws for clinical laboratory parameters
- Urine pregnancy test, for women of childbearing potential
- Practice 6MWT (only required if the subject has not previously performed a 6MWT at the study site; to be conducted following at least 10 minutes of rest [sitting])
- Pulse oximetry (to be performed immediately prior to, throughout the conduct of, and immediately following the 6MWT, if applicable)
- Documentation of supplemental oxygen requirement (L/min)
- Hospitalizations due to a cardiopulmonary indication
- Exacerbations of underlying lung disease
- AEs
- Concomitant medications
- Complete and submit Pre-Baseline Review Form to the Sponsor for Medical Monitor review prior to randomization

7.2 BASELINE/RANDOMIZATION VISIT

All Baseline assessments must be performed prior to the first dose of study drug. Baseline assessments may be conducted over a 48-hour period prior to the first dose of study drug to allow for scheduling of assessments; however, the Baseline 6MWT must occur prior to randomization. The recommended sequence of assessments for the Baseline Visit is as follows (if not combined with the Screening Visit [see Section 7.3 for the recommended sequence of events for the combined Screening/Baseline Visit]):

- SGRQ (questionnaire must be administered prior to any results, procedures, or blood draws)
- Vital signs (following at least 5 minutes of rest; collected prior to 6MWT or after recovery from the 6MWT); including weight, RR, HR, SBP, DBP, and temperature.
- Urine pregnancy test, for women of childbearing potential
- Blood draws for clinical laboratory parameters
- NT-proBNP (must be drawn prior to 6MWT and first dose of study drug; for central laboratory processing only)
- Collection of blood sample for evaluation of biomarkers (optional)
- Collection of blood sample for evaluation of whole genome sequence (optional)
- 12-lead ECG (following at least 5 minutes of rest in the semi-recumbent position)

- Documentation of supplemental oxygen requirement (L/min)
- 6MWT (must be conducted prior to randomization; to be conducted following at least 10 minutes of rest [sitting])
- Pulse oximetry (to be performed immediately prior to, throughout the conduct of, and immediately following the 6MWT)
- PFTs (must be done prior to randomization and after recovery from the Baseline 6MWT)
- Hospitalizations due to a cardiopulmonary indication
- Exacerbations of underlying lung disease
- AEs
- Concomitant medications
- Re-confirm inclusion/exclusion criteria (Baseline 6MWD [not the practice Screening 6MWD] will be used for inclusion/exclusion verification)
- Randomization using IXRS
- Administer study drug and provide dosing instructions and device training (subject must remain in the clinic for at least 1 hour after the first dose of study drug for observation)
- Time to clinical worsening will be evaluated as an exploratory endpoint from the time of randomization until 1 of the following criteria are met:
 - Hospitalization due to a cardiopulmonary indication
 - Decrease in 6MWD > 15% from Baseline directly related to disease under study, at 2 consecutive visits and at least 24 hours apart
 - o Death (all causes)
 - Lung transplantation

7.3 COMBINED SCREENING AND BASELINE

The Screening and Baseline assessments may be conducted in 1 visit if all assessments are performed and all entry criteria are satisfied within 48 hours prior to randomization and dosing of study drug. Baseline PFTs, 6MWT, and CT (if a historical assessment is not available within 6 months prior to randomization) assessments used to determine eligibility criteria may be performed on the same day but prior to randomization. The recommended order of assessments for a combined Screening and Baseline Visit is outlined below.

Assessments to be completed as part of the Screening Visit:

- Informed consent
- SGRQ (questionnaire must be administered prior to any results, procedures, or blood draws)
- Inclusion/exclusion criteria review

- ORHC (Must be performed within 1 year prior to randomization. If a historical RHC is not available in this timeframe, a RHC may be performed during Screening so long as it is performed at least 5 days prior to randomization [Baseline (Day 1)]; a RHC cannot be combined with the Baseline Visit). Select RHC parameters will be recorded in the eCRF including: mPAP, PVR, and PCWP, and vasodilator response (as applicable).
- CT scan (must be performed within 6 months prior to randomization). A redacted copy of the CT scan used to confirm subject eligibility should be sent to the Sponsor.
- Although not required for eligibility, the date of lung biopsy for subjects with a biopsy confirmed diagnosis of ILD will be recorded in the eCRF.
- Blood draws for clinical laboratory parameters (enough blood should be drawn for local laboratory to confirm the entry criteria for hemoglobin, as well as for the complete panel for central laboratory processing)
- NT-proBNP (must be drawn prior to 6MWT and first dose of study drug; for central laboratory processing only)
- Collection of blood sample for evaluation of biomarkers (optional)
- Collection of blood sample for evaluation of whole genome sequence (optional)
- Demographics
- PH history
- Medical history
- PE
- Vital signs (following at least 5 minutes of rest; collected prior to the 6MWT or after recovery from the 6MWT); including height, weight, RR, HR, SBP, DBP, and temperature.
- Documentation of supplemental oxygen requirement (L/min)
- Practice 6MWT to be conducted 1 day prior to Baseline assessments (only required if
 the subject has not previously performed a 6MWT at the study site; to be conducted
 following at least 10 minutes of rest [sitting])
- Hospitalizations due to a cardiopulmonary indication
- Exacerbations of underlying lung disease
- AEs
- Concomitant medications
- Complete and submit the Pre-Baseline Review Form to the Sponsor for Medical Monitor review prior to randomization

Assessments to be completed as part of the Baseline Visit:

- Urine pregnancy test, for women of childbearing potential
- 12-Lead ECG (following at least 5 minutes of rest in the semi-recumbent position)
- 6MWT (must be conducted prior to randomization; to be conducted following at least 10 minutes of rest [sitting])
- Pulse oximetry (to be performed immediately prior to, throughout the conduct of, and immediately following the 6MWT)
- PFTs (must be done prior to randomization and after recovery from the Baseline 6MWT).
- Re-confirm inclusion/exclusion criteria (Baseline 6MWD [not the practice Screening 6MWD] will be used for inclusion/exclusion verification)
- Randomization using IXRS
- Administer study drug and provide dosing instructions and device training (subject must remain in the clinic for at least 1 hour after the first dose of study drug for observation)
- Time to clinical worsening will be evaluated as an exploratory endpoint from the time of randomization until 1 of the following criteria are met:
 - Hospitalization due to a cardiopulmonary indication
 - Decrease in 6MWD > 15% from Baseline directly related to disease under study, at 2 consecutive visits and at least 24 hours apart
 - Death (all causes)
 - Lung transplantation

7.4 TREATMENT PHASE: WEEKS 4, 8, AND 12

The following assessments to be completed during the Treatment Phase:

- Vital signs (following at least 5 minutes of rest; collected prior to 6MWT or after recovery from 6MWT); including weight, RR, HR, SBP, DBP, and temperature.
- Documentation of supplemental oxygen requirement (L/min)
- Urine pregnancy test, for women of childbearing potential
- Blood draws for clinical laboratory parameters (Week 8 only)
- NT-proBNP (must be drawn prior to 6MWT; for central laboratory processing only [Week 8 only])
- Peak 6MWT (must be conducted between 10 to 60 minutes after the most recent dose
 of study drug and following at least 10 minutes of rest [sitting])
- Pulse oximetry (to be performed immediately prior to, throughout the conduct of, and immediately following the 6MWT)
- PFTs (Week 8 only; to be performed after recovery from the 6MWT)
- Hospitalizations due to a cardiopulmonary indication
- Exacerbations of underlying lung disease

- Time to clinical worsening will be evaluated as an exploratory endpoint from the time of randomization until 1 of the following criteria are met:
 - Hospitalization due to a cardiopulmonary indication
 - Decrease in 6MWD > 15% from Baseline directly related to disease under study, at 2 consecutive visits and at least 24 hours apart.
 - Death (all causes)
 - Lung transplantation
- AEs
- Concomitant medications
- Dosing instructions/study drug accountability

Please note the visit window for the Week 4, Week 8, and Week 12 Visits is \pm 5 days.

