3.3.2.4.2 Pregnancy Testing

Females of childbearing potential will undergo a urine pregnancy test at Screening followed by urine pregnancy tests at Baseline and each subsequent study visit (or Baseline Visit if the Screening and Baseline Visits are combined) or ET. A positive pregnancy test will exclude the subject from further participation in the study. Pregnant subjects who are discontinued from the study will be transitioned to an alternate therapy at the discretion of the Investigator.

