4.1 INCLUSION CRITERIA

- 1. Subject voluntarily gives informed consent to participate in the study.
- 2. Males and females aged 18 years or older at the time of informed consent.
 - a. Females of reproductive potential¹ must be non-pregnant (as confirmed by a urine pregnancy test at screening) and non-lactating, and will:
 - i. Either abstain from intercourse (when it is in line with their preferred and usual lifestyle), or
 - ii. Use 2 medically acceptable, highly-effective forms of contraception² for the duration of study, and at least 30 days after discontinuing study drug.
 - b. Males with a partner of childbearing potential must use a condom for the duration of treatment and for at least 48 hours after discontinuing study drug.
- 3. The subject has a confirmed diagnosis of WHO Group 3 PH based on CT imaging, which demonstrates evidence of diffuse parenchymal lung disease performed within 6 months prior to randomization. Subjects may have any form of ILD or CPFE.
- 4. Subjects are required to have a RHC within 1 year prior to randomization with the following documented parameters:
 - a. Pulmonary vascular resistance (PVR) > 3 Wood Units (WU) and
 - b. A pulmonary capillary wedge pressure (PCWP) of \leq 15 mmHg and
 - c. A mean pulmonary arterial pressure (mPAP) of \geq 25 mmHg
- 5. Baseline 6MWD \geq 100 meters.
- 6. Subjects on a chronic medication for underlying lung disease (ie, pirfenidone, nintedanib, etc) must be on a stable and optimized dose for ≥ 30 days prior to randomization.
- 7. In the opinion of the Investigator, the subject is able to communicate effectively with study personnel, and is considered reliable, willing and likely to be cooperative with protocol requirements, including attending all study visits.
- 8. Subjects with connective tissue disease (CTD) must have a Baseline FVC of < 70%.

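### The recommended order for the combined Screening/Baseline visit lists the eligibility CT ahead of the only urine pregnancy test, so a site following it could scan a woman before a test that excludes her

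*Protocol*

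**What the plan says.** Pregnancy status decides eligibility. Inclusion criterion 2a (Protocol 4.1) says that females of reproductive potential "must be non-pregnant (as confirmed by a urine pregnancy test at screening". Section 3.3.2.4.2 adds: "A positive pregnancy test will exclude the subject from further participation in the study". A footnote printed with section 4.2 requires a negative result at Screening and Baseline before study drug is started.

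Three lists in section 7 set out the order of work:

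- **7.1, Screening Visit.** It opens with "The recommended sequence of assessments for the Screening Visit is as follows". RHC and CT are sub-items of the criteria review, where "the following procedures may be performed during the 30 day Screening window if required to satisfy inclusion/exclusion criteria". The urine pregnancy test comes later, after the blood draws.
- **7.2, Baseline Visit.** The pregnancy test is the third entry, ahead of the blood draws. No CT or RHC is listed.
- **7.3, combined visit.** "The recommended order of assessments for a combined Screening and Baseline Visit is outlined below". The CT is in the Screening block, and the section allows it on the same day, before randomization, when no scan from the previous 6 months exists. The entry "Urine pregnancy test, for women of childbearing potential" appears once, at the head of the Baseline block. Section 3.3.2.4.2 likewise ties the test to the Baseline Visit when the visits are combined.

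**The concern.** The CT here is done to establish eligibility, and the urine test can end eligibility. If the CT comes first, a woman with an undiagnosed pregnancy could have imaging that served only the trial and then be excluded on a test that was due at the same visit anyway. The procedure would also be spent on someone who cannot be randomized.

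The protocol plainly uses sequence on purpose elsewhere. The SGRQ precedes any procedure or blood draw, NT-proBNP is drawn before the walk test, and lung function follows recovery from the walk. A site has reason to take the order of the list seriously.

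**Working it through.** No sample size, power or alpha figure bears on this point. The check is one of order and of timing windows.

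**1. Order in 7.3.** After informed consent, the SGRQ and the criteria review with RHC, the list reaches the CT. These entries stand between the CT and the pregnancy test: lung biopsy date, blood draws, NT-proBNP, biomarker sample, genome sample, demographics, PH history, medical history, physical examination, vital signs, oxygen requirement, practice walk, hospitalizations, exacerbations, AEs, concomitant medications and the Pre-Baseline Review Form. That is 17 entries. The test then opens the Baseline block, and the section lists no earlier one.

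**2. Order in 7.1.** Numbering the top-level entries gives: consent 1, criteria review 2 (with RHC and CT beneath it), demographics 3, PH history 4, medical history 5, physical examination 6, vital signs 7, blood draws 8, urine pregnancy test 9. The test is listed after RHC and CT. However, those two procedures are conditional and may fall on any day of the 30-day window, so list position permits the order without fixing it.

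**3. Can an RHC fall inside the combined visit?** Section 7.3 requires a trial RHC at least 5 days before randomization, which is 5 × 24 = 120 hours. The combined assessments must fit within 48 hours before randomization and dosing. Since 120 > 48, the RHC cannot take place at that visit, and the section itself bars combining it with Baseline. For 7.3 the point therefore rests on the CT alone.

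**4. Does anything else put the test first?**

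| Place | What it fixes |
|---|---|
| Protocol 4.1, criterion 2a | Test at screening; no order relative to CT or RHC |
| Protocol footnote printed with 4.2 | Negative test before study drug |
| Protocol 3.3.2.4.2 | Test at Baseline when visits are combined |
| Protocol 3.2, schedule and footnotes | Test marked for Screening, Baseline and the combined visit; CT before randomization; no order between them |
| SAP 12.5.3 | Repeats the visit schedule and says tests are done at study sites; no order |

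The one explicit timing rule guards against exposure to study drug. None of these places covers exposure to a trial CT.

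**The case against.** The strongest reply is that list position is not timing. Both lists are recommendations, and a site can test first and still comply fully. The 7.3 list is also visibly not a strict chronology: it carries an RHC that cannot happen at that visit, a biopsy date taken from records, and a practice walk done the day before. Many subjects will need no new procedure, since section 7.1 says that "previous medical records documenting eligibility criteria may also be used". Criterion 2a already requires the test at screening, and the rule on a negative test before study drug is met under either order.

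Much of this stands, and it limits what can be claimed. A reader might infer any of the following:

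- **The protocol requires CT before the test.** It does not. It recommends an order in which the CT is listed first.
- **An RHC could precede the test within the combined visit.** The 5-day and 48-hour rules exclude this.
- **Section 7.1 fixes the same order.** It leaves the procedures free within the 30-day window.
- **A headcount can be given.** Taking 2% to 10% of 314 gives about 6 to 31, but those percentages are a bare assumption. They would count women who might have a trial procedure, which is not the same as exposed pregnancies.

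The reply leaves the 7.3 order itself unanswered. A same-day CT is expressly allowed, the only listed test comes after it, section 3.3.2.4.2 repeats the Baseline placement, and nothing else closes the gap.

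**Conclusion.** The point holds in a narrow form. At a combined visit, a woman of childbearing potential without a CT from the past 6 months could, at a site that follows the recommended order, have an eligibility CT before the test that would exclude her. In section 7.1 the order is permitted but not required.

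The size cannot be computed. It depends on the share of subjects who are women of reproductive potential, the share of those without an adequate historical scan, and the share of sites that treat the list as a strict sequence. The documents give none of these. The number is likely small, and positive tests among them fewer still. There is no effect on power, alpha, endpoints or any analysis. This is a small patient-safety gap, worth closing because the change costs so little.

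**What to change.** - **7.3:** move the existing urine pregnancy test bullet into the Screening block, after informed consent and the SGRQ and ahead of the CT entry. This keeps the rule that the SGRQ comes before any procedure.
- **7.1:** move the test bullet ahead of the RHC and CT entries.
- **Reconcile** 3.3.2.4.2, criterion 2a in 4.1, the footnote printed with 4.2, 7.1 and 7.3, so that they agree on when the test is done relative to eligibility procedures. In particular, 3.3.2.4.2 now ties the combined-visit test to Baseline while criterion 2a asks for it at screening.

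The reordering moves one bullet in each of two lists and adds no procedure, because the test is already scheduled at the same visits. It is not a proposal for a rule that every trial CT or RHC must follow a negative test. That would be a new clinical rule, and for combined-visit subjects it could require an extra test, since any trial RHC happens days before the visit at which the only listed test is done. How to handle that case is for the sponsor to settle in the reconciliation.

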7.5 TREATMENT PHASE: WEEK 15 (TROUGH)

- Vital signs (following at least 5 minutes of rest; collected prior to 6MWT or after recovery from the 6MWT); including weight, RR, HR, SBP, DBP, and temperature.
- Documentation of supplemental oxygen requirement (L/min)
- Urine pregnancy test, for women of childbearing potential
- Trough 6MWT (at least 4 hours after the last dose of study drug)
- Pulse oximetry (to be performed immediately prior to, throughout the conduct of, and immediately following the 6MWT)
- Hospitalizations due to a cardiopulmonary indication
- Exacerbations of underlying lung disease
- Time to clinical worsening will be evaluated as an exploratory endpoint from the time of randomization until 1 of the following criteria are met:
 - Hospitalization due to a cardiopulmonary indication
 - Decrease in 6MWD > 15% from Baseline directly related to disease under study, at 2 consecutive visits and at least 24 hours apart
 - Death (all causes)
 - Lung transplantation
- AEs
- Concomitant medications
- Dosing instructions/study drug accountability

Please note the visit window for the Week 15 Visit is \pm 5 days and at least 24 hours prior to the Week 16 6MWT. If a subject discontinues study drug prematurely, the subject does not need to return to the clinic for the Week 15 Visit.

7.6 END OF STUDY (WEEK 16) AND/OR EARLY TERMINATION VISIT

The assessments to be completed during the Week 16 Visit are listed below in the recommended sequence of events. If a decision is made to early terminate a subject from study drug or from the study in its entirety, the following assessments should be conducted as soon as possible and prior to study drug discontinuation, if possible. If the subject permanently discontinues study drug prior to Week 16 for any reason, the subject should be encouraged to remain in the study and complete all visits (excluding the Week 15 Visit) up to and including Week 16:

- SGRQ (questionnaire must be administered prior to any results, procedures, or blood draws)
- PE
- Vital signs (following at least 5 minutes of rest; collected prior to 6MWT or after recovery from the 6MWT); including weight, RR, HR, SBP, DBP, and temperature.
- Documentation of supplemental oxygen requirement (L/min)
- 12-Lead ECG (following at least 5 minutes of rest in the semi-recumbent position)
- Urine pregnancy test, for women of childbearing potential
- Blood draws for clinical laboratory parameters
- NT-proBNP (must be drawn prior to 6MWT; for central laboratory processing only)
- Collection of blood sample for evaluation of biomarkers (optional)
- Peak 6MWT (must be conducted between 10 to 60 minutes after the most recent dose of study drug and following at least 10 minutes of rest [sitting])
- Pulse oximetry (to be performed immediately prior to, throughout the conduct of, and immediately following the 6MWT)
- PFTs (to be performed after recovery from the 6MWT)
- Hospitalizations due to a cardiopulmonary indication
- Exacerbations of underlying lung disease
- Time to clinical worsening will be evaluated as an exploratory endpoint from the time of randomization until 1 of the following criteria are met:
 - Hospitalization due to a cardiopulmonary indication
 - Decrease in 6MWD > 15% from Baseline directly related to disease under study, at 2 consecutive visits and at least 24 hours apart
 - o Death (all causes)
 - Lung transplantation
- AEs
- Concomitant medications
- Study drug accountability

Subjects who remain on study drug, complete all assessments during the 16-week Treatment Phase, and meet all eligibility criteria for the open-label extension study (RIN-PH-202) are eligible for an open-label extension study (RIN-PH-202). Additionally, subjects who are withdrawn from study drug prior to Week 16 due to clinical worsening should continue to return to the clinic for scheduled visits (excluding the Week 15 Visit) to be eligible for the open-label study. Refer to Section 7.8 for more information regarding access to the open-label study.

